1 STATEMENT OF COMPLIANCE

The study will be conducted in compliance with the US FDA Title 21 CFR Part 50 – Protection of Human Patients and Part 56 – Institutional Review Boards; the International Council for Harmonisation for Pharmaceuticals for Human Use (ICH) GCP guidelines E6R2 (November 09, 2016) as they apply to observational studies; the Belmont Report; US Title 45 CFR Part 164 Subpart E – Privacy of Individually Identifiable Health Information and the Health Insurance Portability and Accountability Act of 1996 (HIPAA) Privacy Rule (2002); and any applicable national guidelines.

The protocol, informed consent form(s), and all participant's materials will be submitted to the Institutional Review Board (IRB) for review and approval. Approval of both the protocol and the consent form must be obtained before a participating site may enroll participants. Any amendment to the protocol will require review and approval by the IRB before the changes are implemented to the study. In addition, all changes to the consent form will be IRB-approved; a determination will be made regarding whether a new consent needs to be obtained from participants who provided consent, using a previously approved consent form.

The Principal Investigator will assure that no deviation from or changes to the protocol will take place without prior agreement from the registry study sponsor and documented approval from the Institutional Review Board (IRB).

2 PROTOCOL SUMMARY

TITLE:	PATHFINDER I: Post-Market Registry of Auryon Atherectomy Device in Subjects Affected with Infrainguinal Peripheral Artery Disease (PATHFINDER-Registry, EX-PAD-05)
DEVICE DESCRIPTION:	
The AURYON System consists of two sub-units: 1) a single use catheter ("AURYON catheter"); and 2) a laser system.
 
The AURYON catheter is a single use catheter that is made of an array of optic fibers and surrounded by a circumferential blunt blade at its distal tip. The AURYON catheter is connected to the laser system via its connector and transmits energy at pre-set fluence levels of 50 and 60 mJ/mm² to the occluded or narrowed artery. The AURYON System must work over a commercially available 300cm 0.014" guide wire (GW) that crosses the lesion intraluminally. - For the small size catheters (i.e., 0.9mm and 1.5mm), there is a designated lumen tube for a guidewire at the center of the inner blunt blade. Please note that 0.9mm and 1.5mm catheters do not have an aspiration feature and have not been tested in ISR lesions. These devices should not be used in ISR cases. The larger AURYON catheters (i.e., 2.0mm and 2.35mm) have an eccentric guidewire lumen, and include additional features consisting of an aspiration feature (both catheters) and an "off-center" feature (2.35mm only). The aspiration feature is intended for debris and thrombus collection and removal from the vessel during the atherectomy procedure. The "off-center" feature is included in the 2.35 mm catheter only and is designed to facilitate debulking of lesions in blood vessels beyond the catheter's diameter.

INDICATION FOR USE:	The AURYON system is indicated for use in the treatment, including atherectomy, of infra-inguinal stenoses and occlusions, including in-stent restenosis (ISR).
REGULATORY STATUS:	The device is cleared for sale in the US (K181642).
STUDY DESCRIPTION:	The PATHFINDER I Registry is a prospective, non-randomized, single arm, multicenter observational study. It is a pilot registry study towards a subsequent large pivotal phase registry. This pilot registry is aimed to evaluate the performance (peri-procedural) and clinical outcomes (intermediate and long-term) of the AURYON Atherectomy System, within the initial launch phase of the product in the market. After signing an informed consent form, eligible PAD subjects treated with the AURYON Atherectomy

	
System in a post-market (commercial device use) setting will be enrolled and will be followed for 24 months post index procedure.
 
Enrolled subjects will undergo endovascular PAD treatment that includes atherectomy using the AURYON system, according to institutional standard of care. Data collection will include prospective data collection and medical record review of procedures performed according to standard of care, at the study protocol specific follow up time-points.

OBJECTIVES:	To evaluate the safety and efficacy of AURYON Atherectomy System in the treatment of de novo, re-stenotic and ISR lesions in infra-inguinal arteries of Peripheral Artery Diseases (PAD) subjects, in a real-world setting. This is a pilot registry study towards a subsequent large pivotal registry (PATHFINDER II).
ENDPOINTS:	
Primary Endpoints:
 
 1. Primary Efficacy: Acute Procedural Success Percentage of subjects with successful revascularization of target vessel defined as $\leq 30\%$ residual stenosis at the index lesion post atherectomy using the AURYON system and final adjunctive treatment (if required), as evaluated by angiographic corelab. 2. Primary Safety: Percentage of subjects with freedom from peri-procedural major adverse events (PPMAE), defined as (a) flow-limiting dissection, (b) clinically significant distal embolization, (c) bailout stenting, (d) major/unplanned amputation, (e) target vessel perforation requiring endovascular or surgical repair or (f) death, till discharge. 
Secondary endpoint(s):
 
 1. Rate of device related complications requiring intervention, defined as peri procedural MAEs, reported by the operating physician as caused directly due to the use of the AURYON device. 2. Rates of post-discharge MAEs over time; defined as: (a) Unplanned target limb amputation, (b) cardiovascular death, (c) clinically driven target lesion revascularization¹, (d) target vessel revascularization (TVR). 3. Patency rate, defined as (1) $< 50\%$ stenosis at the treated lesion, with peak systolic velocity ratio (PSVR) of < 2.5, as

[figure not shown]
¹ Clinically-Driven Target Lesion Revascularization (CD-TLR), defined as a reintervention performed for $\geq 50\%$ diameter stenosis (confirmed by angiography) within 5 mm of the target lesion after documentation of recurrent clinical symptoms of PAD following the index procedure.

	
assessed quantitatively by Duplex ultrasonography (DUS); OR, (2) for BTK lesions: freedom from occlusion (100% stenosis by DUS) combined with freedom from CD-TLR, at 6, 12, and 24 months.
 
4. Clinical outcomes, defined as change in ankle brachial index (ABI or TBI if needed), walking impairment questionnaire (WIQ), and Rutherford category at 6, 12, and 24, months, compared to baseline
 
Exploratory endpoint(s):
 
1. Intravascular ultrasound assessment pre- and post-Auryon and correlation with angiographic findings (e.g. lesion length, MLA -minimal lumen area gain, calcium severity and removal, etc.). This endpoint will be analyzed only for cases that used IVUS as a routine practice in the index procedure.

STUDY POPULATION:	
Patients with infra-inguinal PAD undergoing atherectomy with the AURYON Atherectomy System.
 
Inclusion Criteria A potential subject will be included in the study if he/she meets all the following inclusion criteria:
 
 1. Subject is ≥ 18 years old. 2. Subject is a candidate for atherectomy for infra-inguinal peripheral artery disease. 3. Documented symptomatic atherosclerotic peripheral artery disease with claudication or critical limb ischemia (CLI) (Rutherford Classification 2-5). 4. Subject is capable and willing to comply with the scheduled follow up 5. Subject is able and willing to sign a written Informed Consent Form (ICF). 
Exclusion Criteria A potential subject will be excluded from the study if he/she meets any of the following exclusion criteria:
 
 1. Target lesion is in an arterial bypass. 2. Planned use of another atherectomy device in the same procedure 3. Co-morbid condition(s) with less than 1yr anticipated survival that could limit the subject's ability to participate in the trial or to comply with follow-up requirements or impact the scientific integrity of the study.

	4. Participating in another study on an interventional non-cleared device, that could impact the study results
DESCRIPTION OF SITES/FACILITIES ENROLLING PARTICIPANTS:	
This study will be conducted at sites where eligible PAD patients are routinely treated with atherectomy by AURYON Atherectomy System.
 
Total enrollment of approximately 100 subjects at approximately 10 sites in the US.
 
To reduce bias by sites, each site may enroll up to 15 eligible subjects whom have successfully completed their index atherectomy treatment with the AURYON system and with analyzable imaging for the primary efficacy analysis.

DESCRIPTION OF STUDY PROCEDURE:	Atherectomy by the AURYON system, of infra-inguinal stenoses, occlusions or in-stent restenosis (ISR).
STUDY DURATION:	The study duration is expected to be two and a half (2.5) years: 6 months to enroll and two (2) years to follow up all subjects.
PARTICIPANT DURATION:	Two (2) years
PRIMARY ANALYSIS PLAN:	
As this is a pilot registry study, no formal hypotheses are defined; rather statistical analyses will be descriptive in nature and will serve to provide estimates of the primary and secondary study endpoints.
 
Also, no formal sample size calculation was performed. The number of enrolled subjects will allow for sufficient safety monitoring and evaluation of the safety and efficacy endpoints and will provide point estimates for the large-scale registry.
 
Analysis sets:
 
Intent-to-treat (ITT) population: The intent-to-treat (ITT) population will consist of all subjects who signed the informed consent form and underwent procedure with an attempt of using the AURYON system.
 
Modified Intent-to-treat (mITT) population: The modified Intent-to-treat (mITT) population will consist of all ITT subjects who underwent atherectomy using the AURYON system for at least one lesion.
 
Per-protocol (PP) population

	
The per-protocol (PP) population will consist of all mITT subjects for whom the AURYON catheter fully crossed at least one target lesion.
 
If a subject does not undergo complete procedure, either due to early or intraoperative non-eligibility of inclusion/exclusion criteria or due to missing evidence of significant arterial disease ($\geq 50\%$) by fluoroscopy angiogram in the index procedure, the subject will be considered as a screen failure. Screen failures will not be included into ITT population and will not be followed or part of the analysis.
 
If a subject undergoes an atherectomy attempt but the AURYON system could not be successfully used in any target lesion, the subject will be included into ITT population but excluded from mITT and PP populations. That subject will not be followed-up after discharge.
 
If a subject undergoes atherectomy using the AURYON system but the AURYON catheter cannot fully cross the target lesion, the subject will be included into ITT and mITT populations but excluded from PP population. That subject will be followed-up after discharge at 30-day, 6-month, 12-month and 24-month visits.
 
Analyses of all primary & secondary endpoints will be conducted in both the mITT and PP populations. The ITT population will serve as the primary set for safety assessments.

RATIONALE FOR NUMBER OF PATIENTS:	
With a total of 100 patients successfully treated by AURYON system in this study cohort, this study will serve as an unpowered pilot registry, towards a larger powered registry study that is planned to include approximately 1000 patients.

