3 STUDY SCHEMA

4 SCHEDULE OF ACTIVITIES

Table 1. Schedule of Events for Screening and Enrollment, AURYON atherectomy Procedure and Post-Procedure Follow-up

Study assessment	Pre-Procedure	Procedure	Post-procedure	Hospital discharge	30 Days (±1 weeks)	6, 12, 24 Months (±1 Month)
Medical history & demographics	X					
Physical Examination	X					X
Informed Consent	X					
Angiographic evaluation of target lesion	X	X	X			
PAD Intervention including AURYON Atherectomy		X				
Quantitative DUS						X
ABI ⁰	X					X
Rutherford Classification	X					X
WIQ	X					X
Record of relevant medications ¹	X	X		X	X ³	X ⁴
Record of PPMAEs ² and other procedural complication		X	X	X		
Record of MAEs ²					X ³	X ⁴

⁰ Toe-brachial index (TBI) will be taken for subjects with non-compressible vessels

¹ Relevant medications: anticoagulant and anti-platelets.

² Adverse events should only be captured after signing of the Informed Consent Form.

³ The visits may be done via phone call for record of any reportable adverse events and relevant medications.

⁴ In case that subject is not showing up to one or more of these follow-up visits, the site should contact the subjects by telephone to collect as much data as possible of any reportable adverse events and relevant medications.

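### Primary safety ends at discharge with no fixed day, and non-cardiovascular death and planned major amputation after discharge enter no listed endpoint

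*Combined protocol and SAP*

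**What the plan says.** Section 2 (Protocol Summary, Endpoints) defines primary safety as the percentage of subjects free of PPMAE. The first three components are "a) flow-limiting dissection, (b) clinically significant distal embolization, (c) bailout stenting". The fourth is amputation, qualified as major/unplanned. The last two, with the window, are "e) target vessel perforation requiring endovascular or surgical repair or (f) death, till discharge". Death carries no restriction on cause, and no day is named.

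Secondary endpoint 1 covers only peri-procedural events that the operator attributes to the device, so it adds nothing after discharge. Secondary endpoint 2 opens with "Rates of post-discharge MAEs over time; defined as: (a) Unplanned target limb amputation, (b) cardiovascular death". It then adds CD-TLR and, last, "d) target vessel revascularization (TVR"). A footnote describes CD-TLR as "defined as a reintervention performed for $\geq 50\%$ diameter stenosis (confirmed by angiography) within 5 mm of the target lesion", once recurrent symptoms have been documented. TVR has no corresponding definition.

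Table 1 in Section 4 follows the same split. PPMAEs "and other procedural complication" are recorded at the procedure, post-procedure and discharge columns only. MAEs are recorded at 30 days (±1 week) and at 6, 12 and 24 months. The 30-day contact may be a phone call. It also takes reportable adverse events, a term not defined in the available text.

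Under the analysis sets in Section 2, ITT is the primary set for safety. Subjects in whom the device was attempted but could not be used belong to ITT, and they have no follow-up after they leave hospital.

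**The concern.** The primary safety figure depends on how long each subject stays in hospital. Treatment follows local standard of care at about 10 sites, and nothing in the plan fixes the length of stay. A non-cardiovascular death on day 5 counts if the subject is still an inpatient. If the subject has gone home, it counts neither in the primary endpoint nor in the list that follows.

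The study is descriptive, so no error rate or decision rule is at risk. What is at stake is what the safety estimates mean. The plan says that the pilot will supply point estimates for a registry of about 1000 patients, yet no listed endpoint gives all-cause mortality after discharge. Subjects up to Rutherford 5 are eligible, so amputation is a relevant outcome, and the plan's wording for it changes at discharge.

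**Working it through.** **No figure to reproduce.** The plan states no event rate, alpha, power or sample-size calculation. The check is a mapping of event types to endpoints, followed by a statement of scale.

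**Mapping.** Inputs are the primary safety endpoint, secondary endpoints 1 and 2, the CD-TLR footnote and Table 1.

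| Event | Before discharge | After discharge, to 24 months |
|---|---|---|
| Cardiovascular death | PPMAE | MAE |
| Non-cardiovascular death | PPMAE | no listed endpoint |
| Unplanned target-limb amputation | PPMAE | MAE |
| Planned major amputation | PPMAE if the slash means *or*; otherwise not counted | no listed endpoint |
| Perforation repair in the target vessel | PPMAE | not CD-TLR unless the stenosis and symptom conditions are met; TVR undetermined |
| Flow-limiting dissection, clinically significant embolization, bailout stenting | PPMAE | not named |
| CD-TLR, TVR | not named | MAE |

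Three things follow.

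1. Non-cardiovascular death changes status at discharge on any reading.
2. Planned major amputation after discharge is uncounted on any reading. Whether that is a *change* at discharge depends on the slash in the PPMAE wording. Read as *or*, a planned major amputation counts in hospital and not later. Read as *major and unplanned*, it never counts.
3. The gap is in event type and not in follow-up time. The 30-day contact does record MAEs, and the uncounted types stay uncounted to 24 months.

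**Scale.** With n = 100, one newly counted subject moves the event-free proportion by 1/100 = 1 percentage point, provided that the subject had not already had a PPMAE.

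For illustration, let p be the true proportion of subjects with a post-discharge event outside every endpoint. The plan gives no value, so every p below is an assumption. The expected number is 100p, and P(at least one) = 1 − (1 − p)^100.

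| Assumed p | Expected number | P(at least one) |
|---|---|---|
| 0.5% | 0.5 | 39.4% |
| 1% | 1 | 63.4% |
| 2% | 2 | 86.7% |
| 3% | 3 | 95.2% |
| 5% | 5 | 99.4% |

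To set this against sampling error, take an illustrative 95/100 event-free, with exact 95% interval 88.7% to 98.4%. Three more subjects counted gives 92/100, with interval 84.8% to 96.5%. The shift is visible, but it is smaller than the width of either interval.

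**The case against.** The strongest reply is that the plan is open about what it measures. The endpoint is labelled peri-procedural, ends at discharge by definition, and is followed by a separate list for later events. Dissection, bailout stenting and perforation mostly arise at the index procedure, so a different list for follow-up is not in itself a fault. This stands. It is why the discharge endpoint can be kept, and why length of stay matters mainly for death and amputation. Leaving out planned amputation may also be deliberate in a population that includes critical limb ischemia. That is possible, but the plan does not say so.

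A reader might go further than the documents allow in four ways.

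- *Late vessel repair counts nowhere.* Not shown: TVR is listed without a stenosis or symptom condition and might capture it.
- *The later list is simply narrower.* It is narrower for death and amputation, but it adds CD-TLR and TVR.
- *Events before day 30 are lost.* Day 30 is not a boundary in the plan for either list, and MAEs are collected at that contact.
- *The reported safety figure is too high by a known amount.* In-hospital freedom and 30-day freedom are different quantities, neither is the true value of the other, and no rates are given. Nor can comparability with the follow-on registry be judged, because its endpoint definitions are not in the document.

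The available text ends at Section 4. A fuller section might define reportable events or TVR. In what is available, no listed endpoint uses the reportable events beyond the MAE list.

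**Conclusion.** The point holds as an inexpensive improvement to a descriptive plan. The primary safety window is each subject's length of stay. After discharge, non-cardiovascular death and planned major amputation enter no listed endpoint through 24 months. The status of a late target-vessel repair cannot be settled from the text.

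The size is about 1 percentage point per newly counted subject, assuming a denominator near 100 and subjects without an earlier PPMAE. Any total beyond that rests on event rates that the plan does not supply. The consequence is for how the safety estimates are read and passed on to the larger registry.

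**What to change.** 1. Keep the discharge endpoint as primary safety. Add a descriptive summary of freedom from the PPMAE components, with all-cause death and any major amputation, through a fixed 30 days.
2. Collect these items, with event dates, at the existing 30-day visit or call. Its window is ±1 week, so a contact can fall on day 30 − 7 = 23. For such subjects, complete the period to day 30 from the next contact.
3. Alongside the post-discharge MAEs, report all-cause death and any major target-limb amputation to 24 months.
4. State whether the slash in the PPMAE amputation component means *or*, and define TVR, including whether a repair for perforation or bleeding counts.
5. Settle the analysis set for the 30-day summary. ITT is the primary safety set, but attempted-and-untreated subjects are not followed after discharge. Either give them one 30-day contact, or state that the summary is limited to the followed (mITT) subjects.

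The cost is a few case report form fields, possibly one extra contact for a small group, and a slightly less favourable safety figure. Replacing the discharge window altogether would be a matter of preference and is not needed.

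### A target lesion that re-occludes and is re-treated before discharge, without a stent or any other listed PPMAE component, counts in no safety endpoint

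*Combined protocol and SAP*

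**What the plan says.** All references are to the Combined protocol and SAP.

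- **Primary safety (section 2, Endpoints).** The measure is "Percentage of subjects with freedom from peri-procedural major adverse events (PPMAE". The components are "a) flow-limiting dissection, (b) clinically significant distal embolization, (c) bailout stenting, (d) major/unplanned amputation" and "e) target vessel perforation requiring endovascular or surgical repair or (f) death, till discharge".
- **Secondary endpoint 1 (section 2).** Device-related complications requiring intervention are "defined as peri procedural MAEs, reported by the operating physician as caused directly due to the use of the AURYON device".
- **Secondary endpoint 2 (section 2).** It opens with "Rates of post-discharge MAEs over time; defined as" and has four items: (a) unplanned amputation of the target limb, (b) cardiovascular death, (c) CD-TLR and (d) TVR.
- **Footnote 1 (section 2).** A CD-TLR is a reintervention for angiographically confirmed stenosis of at least 50% at or near the target lesion, "after documentation of recurrent clinical symptoms of PAD following the index procedure".
- **Secondary endpoint 3, patency (section 2).** Freedom from CD-TLR is part of the definition for below-the-knee (BTK) lesions only. The other definition rests on duplex ultrasound alone.
- **Table 1 (section 4).** PPMAEs "and other procedural complication" are recorded at the procedure, post-procedure and discharge columns. The MAE row is marked only from the 30-day visit.

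**The concern.** Amputation and death are covered on both sides of discharge: PPMAE (d) and (f) before it, MAE (a) and (b) after it. Revascularization of the target lesion or vessel is covered only after it. An early failure of the treated segment can therefore fall between the two composites.

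Take a subject whose final angiogram shows at most 30% residual stenosis. The lesion thromboses that evening and is re-opened before discharge by balloon, thrombectomy, lysis or surgery, with no stent and no other listed complication. The subject is a primary efficacy success, is PPMAE-free and has no MAE. The same reintervention after discharge would have counted.

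The registry tests no hypothesis. Its product is a set of estimates, which section 2 says will inform a registry of about 1000 patients. An estimate that leaves out the earliest reinterventions by definition is too low, and a larger registry using the same definitions would have the same gap.

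**Working it through.** The plan states no rate, margin or power for these endpoints, so there is no figure to reproduce. The check is to run one event through each endpoint.

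**Step 1. Event windows.**

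| Event type | Up to discharge | After discharge |
|---|---|---|
| Amputation | PPMAE (d) | MAE (a) |
| Death | PPMAE (f) | MAE (b), cardiovascular |
| Target lesion or vessel revascularization | no item | MAE (c), (d) |

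**Step 2. Pathways for a re-occlusion re-treated before discharge.**

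| Pathway | Safety endpoint that counts it |
|---|---|
| Caused by a flow-limiting dissection | PPMAE (a) |
| With clinically significant distal embolization | PPMAE (b) |
| Re-treated with an unplanned stent | PPMAE (c) on a plain reading; the term is not defined in the text reviewed |
| Leads to unplanned amputation, perforation needing repair, or death before discharge | PPMAE (d), (e) or (f) |
| Re-treated by balloon, thrombectomy, lysis or surgery, with none of the above | None |

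**Step 3. The last row against the remaining endpoints.**

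- Primary efficacy is scored on residual stenosis after atherectomy and final adjunctive treatment, so the later closure does not alter it.
- Secondary endpoint 1 is restricted to PPMAEs and adds no event type, although its title describes such an event.
- Secondary endpoint 2 begins after discharge.
- Patency could register a BTK case through its CD-TLR condition. A non-BTK lesion that is re-opened in hospital and open on duplex at 6 months counts as patent.

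**Step 4. Size per event.** With n = 100 (section 2 gives approximately 100 subjects), one uncounted event is 1/100 = 1 percentage point on the MAE rate, provided that the subject has no other counted MAE.

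**Step 5. Chance that the gap matters at all.** The documents give no rate p for this pathway, so the values below are assumptions. The chance of at least one event in 100 subjects is 1 − (1 − p)^100.

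| Assumed p | Chance of at least one |
|---|---|
| 0.5% | 39% |
| 1% | 63% |
| 2% | 87% |
| 3% | 95% |

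**Step 6. Scale against sampling error (illustration).** If 2 of 100 subjects have a counted event, freedom from events is 98% (exact 95% CI 93.0 to 99.8). With one more event it is 97% (91.5 to 99.4). The shift is small beside the interval, but it always runs in the favourable direction.

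**The case against.** The strongest reply is that this is an unpowered, descriptive pilot. No test or success criterion depends on the composite, and the choice of components is partly judgement. Many early re-occlusions already count through dissection, embolization, stenting, perforation repair, amputation or death. Table 1 also has a place for other procedural complications up to discharge, so the events may be recorded and could be listed. The text reviewed ends with section 4, so later definitions could not be checked.

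Much of this stands, and it limits the point to the last pathway in the working. It does not remove it. Estimates are what the pilot is for, and no endpoint uses the other-complications record. That category is also undefined, so one cannot be sure that it captures these events.

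Four stronger readings are tempting, and the documents do not support them:

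- *Every re-occlusion re-treated before discharge is missed.* Not so: the pathways with a listed PPMAE component count.
- *Footnote 1 contradicts secondary endpoint 2.* The footnote defines what a CD-TLR is; the endpoint sets the window in which it is counted. Both can hold together.
- *Sites with longer stays look safer.* The documents have no length-of-stay data, and a longer stay also lengthens the PPMAE window. The net direction is not established.
- *The loss is 1 to 3 points, or 17% to 38% of peri-procedural events (1/6 to 3/8, with 1 to 3 missed beside 5 counted).* These rates are assumed, and they treat every in-hospital reintervention as uncounted. At best they are upper bounds under those assumptions.

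**Conclusion.** The gap is real but narrow. As section 2 is written, a re-occlusion re-treated before discharge without a stent or another listed PPMAE component enters no safety endpoint, and for a non-BTK lesion patency need not register it either. The reported reintervention rate is then too low by 1 percentage point per such event at n = 100. The total is unknown, because the documents give no rate for this pathway.

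The conclusion assumes that no later section defines PPMAE or MAE more widely. It also assumes that bailout stenting includes an unplanned stent placed at a return procedure before discharge. If the term is limited to the index session, the gap is wider. The change is worth making because it is cheap and the estimates are to be carried forward.

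**What to change.** In secondary endpoint 2 (section 2), count item (c) CD-TLR and item (d) TVR from the end of the index procedure instead of from discharge. Exclude planned staged procedures, because item (d) as written has no such qualifier and would otherwise count them. Retitle the endpoint, since it would no longer be wholly post-discharge, and state that items (a) and (b) still start at discharge. In Table 1 (section 4), extend the MAE row to the post-procedure and discharge columns.

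Leave the PPMAE list unchanged. Adding a reintervention item there as well would put the missed event into two composites. A return procedure that ends in an unplanned stent could still meet both PPMAE (c) and MAE (d), so define bailout stenting and say how that overlap is reported. The primary safety endpoint will still score the missed event as event-free; the change makes it visible in secondary endpoint 2.

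Cost: an amendment to the endpoint text and the schedule, with IRB approval as section 1 requires, and the matching change in data collection. The reported MAE rate may be slightly less favourable, by 1 percentage point per such event at n = 100. The sample size is unaffected.

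### Patency of non-BTK lesions rests on the visit's duplex scan alone, and no lesion's known failure on an earlier scan or by amputation carries forward, so the reported rate may be overstated

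*Combined protocol and SAP*

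**What the plan says.** The patency definition (section 2 Protocol Summary, Secondary endpoint 3) has two parts, joined as "assessed quantitatively by Duplex ultrasonography (DUS); OR, (2) for BTK lesions: freedom from occlusion (100% stenosis by DUS").

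- **General part:** under 50% "stenosis at the treated lesion, with peak systolic velocity ratio (PSVR) of < 2.5", assessed by DUS. It names no reintervention, amputation or earlier result.
- **BTK part:** "for BTK lesions: freedom from occlusion (100% stenosis by DUS) combined with freedom from CD-TLR, at 6, 12, and 24 months".

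CD-TLR does not depend on DUS. Footnote 1 in section 2 defines it as a reintervention for stenosis of at least 50%, "confirmed by angiography) within 5 mm of the target lesion after documentation of recurrent clinical symptoms of PAD following the index procedure". It is also collected separately, under Secondary endpoint 2: "Rates of post-discharge MAEs over time; defined as: (a) Unplanned target limb amputation, (b) cardiovascular death, (c) clinically driven target lesion revascularization", followed by target vessel revascularization.

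In section 4, Table 1, the row "Quantitative DUS" is marked only in the column for 6, 12 and 24 months. Footnote 4 covers a subject who misses one of these visits: "the site should contact the subjects by telephone to collect as much data as possible of any reportable adverse events and relevant medications".

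Patency, like the other secondary endpoints, is to be analysed in the mITT and PP populations. The summary and schedule do not say how a missing DUS is scored, which lesions form the denominator, or whether a failure at one visit stands at the next.

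**The concern.** The study can know that a lesion has failed without having that visit's scan. The evidence may be a reintervention or amputation recorded as a major adverse event, or a failing DUS at an earlier visit. For non-BTK lesions the definition uses none of it. For BTK lesions it uses only CD-TLR. A lesion found occluded at 6 months and not rescanned therefore has no defined status at 12 or 24 months.

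The definition also fails when a scan is done. A non-BTK lesion that needed reintervention and is open on the next DUS meets the criterion and counts as patent.

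The plan has no hypotheses, so the estimates are its product. Section 2 says they will supply point estimates for the large-scale registry, planned at about 1000 patients. An upward error in patency would pass into that planning.

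**Working it through.** The plan gives no patency rate, scan attendance, CD-TLR rate or BTK share, so there is no figure to reproduce. **Every numerical input below is an assumption**, apart from about 100 subjects (section 2). One lesion per subject is assumed.

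**1. Status of a lesion under the definition as written**

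| What is known at the visit | Non-BTK | BTK |
|---|---|---|
| CD-TLR, no scan | no rule | non-patent |
| Earlier failing DUS, no scan now | no rule | no rule |
| Target limb amputation, no scan | no rule | no rule |
| CD-TLR, then open on DUS | patent | non-patent |

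**2. Size if the rate is taken among scanned lesions**

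Let p be true patency, and a1 and a0 the scan attendance in patent and failed lesions. The scan-only rate is p·a1 / [p·a1 + (1−p)·a0]. With a1 = 80%, the bias in percentage points is:

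| True patency | a0 = 70% | a0 = 60% | a0 = 50% |
|---|---|---|---|
| 60% | +3.2 | +6.7 | +10.6 |
| 70% | +2.7 | +5.7 | +8.9 |
| 80% | +2.1 | +4.2 | +6.5 |

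- Smallest: 0.64/(0.64 + 0.14) = 82.1% against 80%.
- Largest: 0.48/(0.48 + 0.20) = 70.6% against 60%.
- Central: 0.56/(0.56 + 0.18) = 75.7% against 70%. Of 100 lesions 74 are scanned, so the standard error is √(0.757 × 0.243/74) = 5.0 points and the bias is 1.1 standard errors.

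**3. How the BTK clause reduces it**

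Take p = 70% and 10 of 100 lesions failed by CD-TLR without a scan, spread in proportion to the BTK share b. The BTK ones are scored and the others are dropped. The rate is 70/[100 − 10(1−b)]: 77.8% for b = 0, 75.3% for 30%, 73.7% for 50%, and 70.0% (no bias) for 100%.

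**4. How far the result depends on the unstated rule**

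Take p = 70%, 10 known failures without a scan, and 20% of the other 90 scans missing at random. That leaves 72 scanned lesions, 56 of them patent.

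- Unscanned lesions excluded: 56/72 = 77.8%.
- Known failures kept as non-patent: 56/82 = 68.3%.
- Every missing scan counted as failure: 56/100 = 56.0%.

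**5. Retreated lesions that are open on DUS**

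With all 100 lesions scanned and true patency of 70%, 5 retreated and open non-BTK lesions give (70 + 5)/100 = 75%.

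**6. How possible remedies behave**

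A three-visit simulation (400,000 subjects) assumed:

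- loss of 12, 10 and 12% per interval;
- death of 2, 3 and 6% per interval;
- half of losses known clinically without DUS;
- attendance of 80% in patent and 60% in failed lesions.

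True patency among survivors is 0.88, then 0.88 × 0.90 = 0.792, then 0.792 × 0.88 = 0.697.

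| Estimate | 6 months | 12 months | 24 months |
|---|---|---|---|
| True, among survivors | 88.0% | 79.2% | 69.7% |
| Scanned lesions only | 90.7% | 83.5% | 75.4% |
| Scanned, plus known losses in the denominator | 88.0% | 77.8% | 67.1% |

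Adding known losses to the denominator runs low later, because known losses always count while only 80% of patent lesions do. Time to first loss dated at detection, with death competing, gave 90.3% and 81.8% at 6 and 12 months. That is about 2 points high, because losses not known clinically wait for a scan to be dated.

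**The case against.** A reader might infer that patency can be scored only from the visit's scan for every lesion. The text does not support that. A BTK lesion with CD-TLR is non-patent with no scan, because CD-TLR is confirmed by angiography and can be learned by telephone. The wording even leaves some room for the CD-TLR clause to govern both parts; if it does, the gap shrinks to earlier failing scans and amputations.

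A reader might also infer that the plan drops unscanned lesions, so that patency is certainly overstated. Nothing says so. The named populations are mITT and PP, not a scanned subset, and counting missing scans as failures would push the rate down. Exclusion is only the natural complete-case reading of a DUS-based rate.

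Lower attendance after failure is likewise assumed. Subjects with recurrent symptoms may be seen more often, and section 2 provides for medical record review, which could recover some scans. The simulated bias grows across visits only because a fixed attendance gap meets falling patency; it is not independent evidence.

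The survival criterion ("Co-morbid condition(s) with less than 1yr anticipated survival") allows deaths before 24 months, but a death is not a known patency failure. It shows only that death needs a rule.

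Finally, the endpoint is secondary and descriptive, and CD-TLR and unplanned amputation are reported under Secondary endpoint 2, so those failures are not hidden. That limits the severity. It does not give the patency rate a defined denominator or correct its treatment of retreated lesions.

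**Conclusion.** The point holds in this form: the general part of the definition omits CD-TLR, no lesion carries an earlier failing DUS or an amputation forward, and the telephone fallback creates visits where a failure is known but cannot be scored. The misclassification of retreated, open non-BTK lesions follows from the definition itself and needs no assumption about missing scans.

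Upward bias is conditional. It requires reporting among scanned lesions and poorer attendance after failure. Under the assumed ranges it is about +2 to +11 points, and smaller the more of the unscanned failures are BTK lesions with CD-TLR. The change should be made, at a priority suited to a secondary endpoint in a pilot. The available text is the protocol summary and schedule; a fuller rule in a later section, if there is one, would settle the point.

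**What to change.** 1. Apply freedom from CD-TLR to both parts of the definition.
2. Count a lesion as non-patent from the first of a failing DUS, a CD-TLR known from any source (including the telephone contact), or target limb amputation. State which amputations count, since the adverse event list names unplanned ones. Carry that status to all later visits, rescanned or not.
3. Report patency at 6, 12 and 24 months with 95% confidence intervals in mITT and PP from a time-to-first-loss estimate. Allow for losses being found only at visits, either by interval censoring or by stating that loss is dated at detection. Treat death as a competing event, and note that one minus cumulative incidence then counts deaths without loss as not lost.
4. At each visit, give the numbers scanned, known lost without a scan, dead and unknown. Keep the scan-only rate as a supportive figure.

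Items 1, 2 and 4 are the core. The model in item 3 is one workable choice. Simply adding known losses to the scanned denominator is simpler, but ran low at 24 months in the simulation.

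The cost is endpoint and analysis wording, a little more analysis work, and a somewhat lower stated patency rate. DUS, adverse event records and telephone contacts are already collected.
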